18.6.2. Sponsors reporting responsibilities

It is the responsibility of sponsor to ensure that the following are reported to national regulatory authorities and ethics committees, as applicable, immediately, but no later than seven calendar days following the date of awareness by sponsor.

- All serious adverse events.

CONFIDENTIAL

- All serious adverse device effects.
- All device deficiencies that could have led to serious adverse events but did not because suitable action was taken, intervention had been made or because of fortunate circumstances.
- New findings and/or updates in relation to already reported events.

If the serious adverse event results in imminent risk of death, serious injury, or serious illness that requires prompt remedial action for other subjects, users or other persons or a new finding to such a serious adverse event, sponsor must immediately but no later than two calendar days after awareness by sponsor report the event to national regulatory authorities and ethics committees, as applicable.

It is the responsibility of sponsor to inform all investigators in writing within ten working days if device deficiencies, adverse events, adverse device effects, near-incidents, serious adverse events, serious adverse device effects or unanticipated serious adverse device effects lead to corrective actions (e.g. change of IFU).

18.6.2.1 Medical Advisor Safety Review

The Sponsor is responsible for ensuring all Serious Adverse Event (s) are provided to the Medical Advisor for review and discussion.

The Medical Advisor will be informed of the following:

- All serious adverse events related to the investigation product or clinical investigation and serious adverse device effects
- A device deficiency that could have led to a serious adverse event but did not because suitable action was taken, intervention had been made or because of fortunate circumstances
- New findings and/or updates in relation to already reported serious events

In addition, the Medical Advisor will receive lists of any reported AE's and ADE's related to the investigation product or clinical investigation, as defined by sponsor for a review of safety.

Correspondence, decisions and recommendations regarding safety in the Clinical Investigation from the Medical Advisor must be documented and saved electronically in the Sponsor File.

18.6.2.2 Data Safety and Monitoring Board

The review of all safety data will be conducted on an ongoing basis to identify any potential safety issues. If needed, the Medical Advisor can call for a Data Safety and Monitoring Board meeting with relevant members, to discuss potential safety issues and further recommendations, if relevant.

Based on the safety data review, the Medical Advisor along with the DSMB may recommend that the sponsor modifies, temporarily suspends or terminates the clinical investigation.

Correspondence, decisions and recommendations regarding safety in the Clinical Investigation from the Data Safety and Monitoring Board must be documented in meeting minutes and saved electronically in the Sponsor File.

CONFIDENTIAL

All final decisions, however, regarding clinical investigation modifications, remain with the Sponsor.

19. Suspension or premature termination of the clinical investigation

Sponsor may suspend or prematurely terminate an investigation site or the entire clinical investigation for documented significant reasons.

If a suspicion of an unacceptable risk to subjects develops during the clinical investigation, sponsor will suspend the investigation while the risk is assessed. Sponsor will terminate the investigation if an unacceptable risk is confirmed. Sponsor will ensure that the premature termination will be justified in writing and will promptly inform the regulatory authorities and relevant EC(s). If monitoring or auditing of the clinical investigation identifies serious or repeated deviations at one of the participating investigation sites, sponsor will suspend or terminate the particular investigation site. The sponsor or investigator will inform the regulatory authority as appropriate and notify the EC about the termination of the site.

If suspension or termination of the clinical investigation occurs, the investigator(s) will promptly inform the enrolled subjects. Sponsor will provide resources to fulfil the obligations from the CIP for follow-up of the subjects as necessary.

20. Clinical investigation report

At completion of the investigation sponsor is responsible for writing the clinical investigation report. The report is retained on file. The report contains a critical evaluation of all data, which have been collected during the investigation. The report describes the methodology and design as well as the data analyses, including statistical results and conclusions.

Sponsor and national coordinating investigators must sign the final version of the clinical investigation report or an affidavit, indicating their agreement with the contents. If no coordinating investigators are appointed, then the signatures of the principal investigators should be obtained.

The clinical investigation report must be submitted to EC and regulatory authorities.

21. Publication policy

Coloplast, sponsor, is referring to the internal document 'Clinical Publication Policy' that will be available for internal and external persons involved in the publication process.

The investigation will be registered on a public accessible database, e.g. www.ClinicalTrial.gov, before recruitment of the first subject. The results of the investigation, positive as well as inconclusive and negative will be published in the same public accessible database. The subjects' identity will remain confidential. Publication of results in the database will be conducted per the law of personal data protection and will be initiated as soon as scientifically acceptable, however, within one year after the last subject has completed the investigation. Data from the investigation is considered confidential until it is published per the conditions of this CIP and the 'Clinical Publication Policy'. Sponsor may publish anonymous single subject case stories (or public, if the subject consents) at any time during and after the investigation. The identification of the participant must not be possible. Sponsor reserves the right to use the data (published and unpublished) for reimbursement or regulatory purposes.

CONFIDENTIAL

22. Appendix

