4.6. Blinding

No blinding will be used in this investigation, as it is not possible to blind the products due to visible differences.

CONFIDENTIAL

5. Investigational products

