6.2. Recruitment and enrolment

The recruitment of potential subjects will commence only once authorisation has been received from the Regulatory Authorities and the EC.

Table 2: Table showing an overview of the recruitment process

Recruitment method	Coloplast Database	Advertisement	Patient records
Potential subjects	Recruitment will go through Coloplast' own subject database (stoma care users), and a "landingpage" at Coloplast website. Potential subjects are identified by the following searching criteria in the Coloplast database: 
• Has an ileostomy or colostomy	Advertisement i.e. in local shops, sports facilities, local newspapers, social media and stoma associations. The advertisement will state the contact information of relevant Principal Investigator(s) to contact or the web-address for a Coloplast 'recruitment landing page'. A CRO may help by receiving reply	Recruitment from hospitals, home care nurses and outpatient stoma clinics will be via patient visit or screening of subject records kept at the participating sites.

CONFIDENTIAL

	
 • Be at least 18 years of age 	letters-mails and/or answering the phone from interested subjects.	
First contact	
The identified potential subjects will as first contact be sent an Invitation and Reply Letter by mail or email.
 
If a potential subject does not return the reply letter or answer the email, they may be contacted by phone, mail or email to make sure that they have received the approach.
	
Interested subject contact the investigator.
	
The identified potential subjects will be contacted and informed about the investigation by the investigator (via telephone, letter or e-mail).

Second contact	
If potential subjects return the Reply Letter/reply to the email, or have called the investigator as first contact and are interested, the Investigator or delegated site personnel will contact the subjects by phone and give a short introduction to the investigation and go over the inclusion and exclusion criteria.
 
If the subjects do not meet the inclusion criteria or meet the exclusion criteria, this will be registered at the Subject Screening Log.
		

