7.3. Case Report Forms

All assessments and observations throughout the investigation for each subject must be carefully recorded in an electronic CRF (eCRF) or an application (Clinical trial App) in a provided phone for each subject.

Assessments completed by the principal Investigator, or delegate, will be recorded in the eCRF. Questions completed by the subject at visits or at every product (1pc) or baseplate change (2pc) will be recorded in the Clinical Trial App. All data completed in the Clinical Trial App will be uploaded directly to the data base when the phone is on a network.

CRFs will be completed by the subject, and/or by the principal investigator, or delegate, who have signed the Site Personnel Signature and Delegation List and Clinical Investigation Training Log.

It is the responsibility of the Investigator that all data and observations are entered promptly and correctly.

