11.2. Sample size

The itching score is given at each baseplate change and the max of these scores per week at steady state is the primary endpoint. The max score is only calculated if there are measurement for more than four days within a week. For each subject approximately three measurements will be available for each test period.

The sample size calculation is based on a simplified linear mixed model with only 1-pc users and no period effect (corresponding to the design from CP300). The model includes a fixed effect of product (comparator and test product), a random effect of subject and a random interaction effect of product and subject.

Based on data from CP300 it is assumed that the total standard deviation of the primary endpoint is 1.82 and that the total variation 1.82² is divided so that:

- a random effect of subject accounts for 68% of the total variation
- a random interaction effect of product and subject accounts for 0%
- and the residual accounts for 32% of the total variation

In table 1 the needed sample size is calculated by simulation for varying values of the true difference between comparator and test product regarding mean max itching score per week and for different values of the power to demonstrate that the difference is significantly different from 0.

Table 4: Subjects needed for comparing mean max itching score between two products

True difference	Reduction in mean if the mean for the comparator is 2.2 as for [REDACTED] in CP300	Power		
		0.8	0.85	0.9
0.6	27%	46	>46	>46
0.7	32%	35	40	45
0.8	36%	30	32	36

Based on the numbers in the table, 40 subjects should test each product to ensure a power of 85%, if the true difference between the comparator product and a test product is 0.7 (corresponding to a 32% reduction if the mean for the comparator is 2.2 as in CP300). This will be enough when comparing the two products. 1-pc and 2-pc users will be evaluated separately (in a combined model). As there are no previous data for 2-pc users the sample size calculations for 1-pc users is assumed to cover 2-pc users as well. To take a potential drop-out (20%) into account it is recommended to include a total of 48 1-pc and 48 2-pc users, resulting in a total of 96 subjects.

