11.5. Interim analysis

There is no planned interim analysis in this investigation that will affect the evaluation of the primary objective. To facilitate the evaluation of the secondary objective regarding evaluation of the [REDACTED] [REDACTED] a data migration will be provided to the external partner [REDACTED] before DBL. The data migration will be based on data from all subjects having finalized visit 2. Any results of the analyses of data from [REDACTED] before DBL will be for the use of [REDACTED] only and not reported to Coloplast A/S.

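### Section 21 lets the sponsor publish single-subject case stories while an open-label trial with subject-reported endpoints is still running; hold them until database lock

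*Combined protocol and SAP*

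**What the plan says.** Section 21 of the protocol contains three statements that matter here.

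- A general rule: "Data from the investigation is considered confidential until it is published per the conditions of this CIP", and per an internal publication policy that is named but not reproduced.
- Directly after it, a permission: "Sponsor may publish anonymous single subject case stories (or public, if the subject consents) at any time during and after the investigation".
- Directly after that, a sentence requiring that the participant cannot be identified.

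No section available to us delays case stories until the last subject is out or the database is locked, and none limits what they may say about product, outcome or preference.

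Section 4.6 says: "No blinding will be used in this investigation, as it is not possible to blind the products due to visible differences". Section 11.2 defines the primary endpoint: "The itching score is given at each baseplate change and the max of these scores per week at steady state is the primary endpoint". Section 7.3 says who supplies the ratings: "Questions completed by the subject at visits or at every product (1pc) or baseplate change (2pc) will be recorded in the Clinical Trial App". Appendix 1 shows that the subject gives the itch rating and the sponsor derives the weekly maximum.

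Section 6.2 recruits through the sponsor's own database of stoma-care users, a landing page on its website, patient records at the sites, and advertising: "Advertisement i.e. in local shops, sports facilities, local newspapers, social media and stoma associations".

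**The concern.** When ratings are subjective and the product is known, what subjects expect of the product can enter the score. An open-label design accepts some of this. A published account of one participant's experience with the new baseplate, issued by the sponsor while others are still scoring, would add a source of expectation that the sponsor controls and the trial does not need.

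If such a story favoured the test product, it would move ratings of that product and not of the comparator. Making each subject his or her own control removes stable differences between subjects. It does not remove a shift tied to one product, because that shift is part of the product contrast being estimated. The product-by-period interaction in section 11.1 is there for carry-over, and a shift of the same size in both periods would not show in it.

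The exposed endpoints are the primary endpoint, the other symptom ratings and frequencies, feeling of security, handling, quality of life and preference. Section 11.4 counts the purpose as fulfilled if any one skin endpoint differs significantly, and section 11.1 applies no multiplicity adjustment, so even a modest shift could matter.

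**Working it through.** **1. Is the permission limited elsewhere?** The confidentiality rule in section 21 lasts until data are published under the protocol's own conditions, and the case-story sentence is one of those conditions. The rule therefore does not restrain it. Section 7.1.1 limits what subjects are told to the product for the coming period, which does not touch published material. No other visible section sets a limit.

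**2. How much is subject-reported?** Section 11.1 shows 17 secondary endpoints in unredacted text:

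| Type | Number | Reported by the subject? |
|---|---|---|
| 0–10 ratings (pain, burning, discomfort, moving around, sticking the baseplate) | 5 | yes |
| Yes/no items (bleeding, weeping or moisture, ulcers or sores) | 3 | yes |
| 14-day frequencies (itching, pain, burning) | 3 | yes |
| Discoloration area and intensity, from photos | 2 | no |
| DET total and three item scores | 4 | investigator-assessed |

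So 5 + 3 + 3 = 11 of 17 are subject-reported, and 5 of 17 are 0–10 ratings.

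**3. When could a story matter?** Inputs: enrolment over about six weeks (section 6.2), two periods of 42 days (section 4.1), steady state in the last three weeks of each period (Appendix 1). Assumptions: uniform enrolment and 84 days per subject. Steady-state scoring then falls in weeks 3–6 and 9–12 after entry. The first subject ends period 1 at week 6 and completes at week 12. The last subject completes at week 18.

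- Story at week 6: 75% of period 1 scoring and 100% of period 2 scoring still lie ahead. (0.75 + 1.00)/2 = 87.5%.
- Story at week 12: none of period 1 and 75% of period 2 lie ahead. (0 + 0.75)/2 = 37.5%.

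**4. The plan's own sample size figure.** Section 11.2 gives a total SD of 1.82, a residual share of 32%, a product-by-subject share of 0%, a difference of 0.7, and 40 subjects for 85% power. For a two-sided 5% within-subject comparison with m weekly maxima per period:

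Variance of a subject's difference = 2 × 0.32 × 1.82² / m = 2.120 / m.

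- m = 1: SD = 1.456; SE at N = 40 is 1.456/√40 = 0.230. By the non-central t, power is 84.3%, and 41 subjects are needed for 85%. This approximately reproduces the stated 40.
- m = 3, the number section 11.2 says to expect: SD = 0.841; SE = 0.133. Power is 99.9%, and 15 subjects are needed.

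The difference between the two is a separate matter. Both values are carried below.

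**5. What an assumed shift would do.** With no true product difference, N = 40, and a mean shift b in the product contrast, the chance of a significant result is the non-central t probability with non-centrality b/SE:

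| Assumed mean shift b | m = 1 | m = 3 |
|---|---|---|
| 0 | 5% | 5% |
| 0.1 | 7% | 11% |
| 0.2 | 14% | 31% |
| 0.3 | 25% | 60% |

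The mean shift is the share of subjects exposed times the shift in their test-product rating. With 10–30% exposed and a shift of 0.5–1.0 point, 0.10 × 0.5 = 0.05 and 0.30 × 1.0 = 0.30. Against the 0.7 points the trial is sized on, that is 0.05/0.7 = 7% to 0.30/0.7 = 43%. Neither the exposed share nor the size of shift comes from the documents.

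**The case against.** The strongest reply is that this is a chain of conditions. The clause allows publication and no section plans a story. Harm needs a story to appear, to favour the test product, and to be seen by subjects before they finish scoring. The internal publication policy may already restrict timing or content. The design also accepts open-label expectation bias in any case. All of this stands, and it keeps the point at the level of a cheap improvement. It does not answer why the protocol should expressly allow publication during conduct.

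Several stronger readings are tempting, and the documents do not support them:

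- *Sites score the primary endpoint.* They do not. Sites could be influenced only indirectly, through training, calls and the DET assessment.
- *Most secondary endpoints are 0–10 self-ratings.* Only 5 of the 17 visible ones are. The supportable statement is that 11 of 17 are subject-reported in some form.
- *The clause breaches the plan's own safeguards.* The confidentiality rule yields to the protocol's publication conditions. The restriction in section 11.5, "only and not reported to Coloplast A/S", concerns the external partner's analyses before lock. It does not keep trial data from the sponsor, whose clinical manager reviews eCRF and app data throughout (section 9.1).
- *Identifiable stories are plainly allowed.* The clause allows public stories with consent and the next sentence forbids identification. The section contradicts itself.
- *The whole of January to May 2020 is exposed.* A story needs someone who has already used the product. The first subject finishes period 1 at about week 6, when enrolment is closing, so an effect on enrolment would be slight.
- *The 7–43% is an estimate of bias.* It only restates assumed inputs.

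**Conclusion.** The point holds as a conditional risk. The protocol permits single-subject stories during conduct, in an unblinded trial whose primary endpoint and many other endpoints rest on subjects' own reports and which recruits partly through channels such stories could reach. A favourable story before scoring ends could bias the product contrast, and the cross-over gives no protection.

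The size is unknown. The documents contain no figure for exposure or for any rating shift, so the false-positive rates above show sensitivity only. They rest on the plan's variance inputs, 40 subjects, no true difference and assumed mean shifts of 0.1 to 0.3 points. The timing shares rest on uniform enrolment. The documents do not show that a story was intended or that bias would occur. A hold would leave the sample size and the analysis unchanged.

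**What to change.** In section 21, change the timing in the case-story sentence so that stories may be published only after the last subject has completed and the database is locked. In the same edit, reconcile the allowance for public stories with consent and the sentence that rules out identification. If the internal publication policy already imposes such a hold, state it in the protocol.

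Limit the hold to publication. A wider ban on releasing individual outcomes or photos before lock would not be workable. Investigators assess and photograph the skin (section 7.1.1), subjects can see their own app entries (section 10) and request their data (section 16.2), safety reporting must continue (section 18.6), and a transfer to the external partner before lock is planned (section 11.5). None of these should be restricted.

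The cost is a short text change and a delay of case stories until database lock. No scientific information is lost.

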22.1. Appendix 1 - Endpoints

The column "Description of endpoints" includes endpoints where the corresponding analysis is described in the statistical analysis section. The column "Measurement" includes measurements that will be summarized and/or listed. The column "Derived from" describes the questions in the eCRF/APP or the method used as basis for the endpoint or measurement. The three last weeks in each test period is in the table referred to as "steady state".

[figure not shown]
Type of endpoint	Group of endpoint	Description of measurement	Derived from	Origin	Assessed by	V1	V2	V3	Calls	Product change
Primary	Itching	1. Max itching score within a week at steady state	The individual itching score per baseplate on a scale from 0-10 (see question below)	Skin condition	Sponsor					X
	Secondary	Max itching score per baseplate change (0-10) at steady state	How much of the time have you experienced any itching around your stoma since you last changed your product? (tick one box only)	Skin condition	Subject					X
		Frequency of itching per baseplate change at steady state	
 None of the time A little of the time Some of the time A lot of the time All of the time 							
			Please rate how itchy the skin around your stoma has been at its worst since you last changed your product (tick one box only) (Scale from 1-10, very mild itch - worst itch possible)							
		2. Frequency of itching in	How often have you experienced itchy skin around your stoma in the past 14 days?	Subject	Subject (Visit CRF)					X

CONFIDENTIAL

Type of endpoint	Group of endpoint	Description of Measurement	Derived from	Origin	Assessed by	V1	V2	V3	Calls	Product change
			
 None of the time A little of the time Some of the time A lot of the time All of the time 							
Pain	3. Max pain score within a week at steady state	The individual pain score per baseplate on a scale from 0-10 (see question below)	
Skin condition
 	
Sponsor
						
		
Max pain score per baseplate change (0-10) at steady state
 
Frequency of pain per baseplate change at steady state
	
How much of the time have you experienced any pain around your stoma since you last changed your product? (tick one box only)
 
 None of the time A little of the time Some of the time A lot of the time All of the time 
Please rate how painful the skin around your stoma has been at its worst since you last changed your product (tick one box only)
 
(Scale from 1-10, very mild pain – worst pain possible)
 
How often have you experienced any pain in the skin around the stoma in the past 14 days?
	
Subject
 						
	4. Frequency of pain in the past 14 days									

CONFIDENTIAL

Type of endpoint	Group of endpoint	Description of Measurement	Derived from	Origin	Assessed by	V1	V2	V3	Calls	Product change
		days by end of treatment	
 None of the time A little of the time Some of the time A lot of the time All of the time 							X
Burning	5. Max burning score within a week at steady state	
The individual burning score per baseplate on a scale from 0-10 (see question below)
 
Max burning score per baseplate change (0-10) at steady state
 
Frequency of burning per baseplate change at steady state
	
Skin condition
  
Skin condition
  
Subject
 
How much of the time have you experienced any burning feelings from the skin around your stoma since you last changed your product? (tick one box only)
 
Please rate any burning feelings from the skin around your stoma at its worst since you last changed your product (tick one box only)
 
(Scale from 1-10, very mild burning – worst burning possible)
							

CONFIDENTIAL

CONFIDENTIAL

Type of endpoint	Group of endpoint	Description of Measurement	Derived from	Origen	Assessed by	V1	V2	V3	Calls	Product change
	9.	per baseplate change at steady state	changing your product? (tick one box only) (Experiencing/Not experiencing)							X
Overall physical discomfort	10.	Max overall physical discomfort score within a week at steady state	The individual overall physical discomfort score per baseplate on a scale from 0-10 (see question below)	Skin condition	Sponsor					X
		Max overall physical discomfort per baseplate change (0-10) at steady state	How would you rate your overall physical discomfort from skin around your stoma since you last changed your product? (tick one box only) (11-point scale from No discomfort to A lot of discomfort)	Skin condition	Subject					
Overall ability to move around	11.	Max overall ability to move around score within a week at steady state	The individual overall ability to move around score per baseplate on a scale from 0-10 (see question below)	Skin condition	Sponsor					X
		Max overall ability to move around per baseplate change (0-10) at steady state	How much have skin complications around your stoma caused you difficulty in your overall ability to move around since you last changed your product? For example,	Skin condition	Subject					X

CONFIDENTIAL

Type of endpoint	Group of endpoint	Description of Measurement	Derived from	Origin	Assessed by	V1	V2	V3	Calls	Product change
Overall ability to stick the stoma bag adhesive to your skin	12. Max overall ability to stick the stoma bag adhesive to your skin score within a week at steady state	The individual Overall ability to move around score per baseplate on a scale from 0-10 (see question below)	Skin condition	Sponsor						
Discoloration (DET score also includes a discoloration endpoint	13. Discoloration area score (cm^2) per baseplate change at steady state	Max overall ability to stick the stoma bag adhesive to your skin change (0-10) score per baseplate at steady state	Skin condition	Subject						
Intensity	14. Intensity score (cm^2) in the inner zone per baseplate change at steady state	Based on discoloration area in different zones close to the stoma estimated by [REDACTED] from photos of the skin	Skin condition (photos of skin)	Sponsor, from photos taken by subject						
		Based on area with a given intensity estimated by [REDACTED] from photos of the skin	Skin condition (photos of skin)	Sponsor, from photos taken by subjects						

CONFIDENTIAL

CONFIDENTIAL

Type of endpoint	Group of endpoint	Description of endpoint	Measurement	Derived from	Origin	Assessed by	V1	V2	V3	Calls	Product change
Explorative endpoints		end of treatment									
		Is there discoloration of peristomal skin with complications? (Yes/No) by end of treatment	Is there discoloration of peristomal skin with complications? (pain, shiny, indurated, hot, itching, burning)? (Yes/no)	Skin condition (DET score)	Investigator (subject)	X	X	X			
		Is there damage to the lower layers of the skin with complications? (moisture, bleeding or ulceration)? (Yes/no)	Is there damage to the lower layers of the skin with complications (moisture, bleeding or ulceration)? (Yes/no)	Skin condition (DET score)	Investigator	X	X	X			
		Is there raised tissue above skin level with complications? (bleeding, pain or moisture)? (Yes/no)	Is there raised tissue above skin level with complications (bleeding, pain or moisture)? (Yes/no)	Skin condition (DET score)	Investigator (Subject)	X	X	X			
		Stoma behaviour	Did your stoma behave differently from normal since your last visit/call? (Yes/No)	Visit CRF	Subject	X	X	X			
			-If yes, please specify	Visit CRF	Subject	X	X	X			
			How was the feeling of security while wearing the product? (5-point scale from Very poor to Very good)	Visit CRF	Subject	X	X	X			
				How did you find cutting the baseplate? (5-point scale from very difficult to very easy)	Visit CRF	Subject	X	X			
Handling		21. Feeling of security									
		22. Cutting the baseplate	(5-point scale by)	end of treatment	Visit CRF	Subject	X	X			

CONFIDENTIAL

CONFIDENTIAL

Type of endpoint	Group of endpoint	Description of Measurement	Derived from	Origin	Assessed by	V1	V2	V3	Calls	Product change
		change at steady state	Estimated by [REDACTED] from photos of the baseplate	Leakage (photos of baseplate)	Sponsor, from photos taken by subjects	X	X	X		
		29. Leakage area (cm ²) by baseplate								
		change at steady state								
		30. Total HQoL score (0-92) by end of treatment	Calculated based on the questions from the Quality of life questionnaire	Quality of life questionnaire (Ostomy-Q)	Subject fills in the questions and the sponsor calculates the score	X	X	X		
		31. Discreetness score (0-24) by end of treatment								
		32. Comfort score (0-24) by end of treatment								
		33. Confidence (0-24) score by end of treatment								
		34. Social life (0-20) score by end of treatment								
Preference		35. Proportion of preference of test product or SC?	Which product do you prefer? (The product from the first test period, the product from the second test period?)	Visit CRF	Subject	X				

CONFIDENTIAL

CONFIDENTIAL

[figure not shown]
Type of endpoint	Group of endpoint	Description of Measurement endpoint	Derived from	Origin	Assessed by	V1	V2	V3	Calls	Product change
Reason for change		(You may tick more than one box)								
		What was the main reason for changing the products? (14 choices + other text)	App							
		
 - I followed my usual changing pattern - I thought it would be nice with a clean product - In preparation of an activity (i.e. going out, doing sports, travelling) - The entire baseplate had become detached - The outer edge of the baseplate had become detached - The centre of the baseplate had become detached - I was afraid the baseplate would become detached - The area around the stoma was itching - The area around the stoma was painful - There was leakage underneath and outside the baseplate - There was leakage underneath the baseplate (but not outside the baseplate) 	Subject							

CONFIDENTIAL

Type of endpoint	Group of endpoint	Description of measurement	Derived from	Origin	Assessed by	V1	V2	V3	Calls	Product change
			
 - The bag was full of air (ballooning) - There was vacuum in the bag (pancaking) - Due to test visit in the investigation - Other reason (text) 							
		Was there leakage outside the baseplate? (Yes/no) by baseplate change at steady state	Was there leakage outside the baseplate (i.e. soiling the clothes)? (Yes/no)	APP					Subject	
		Accessories used? by baseplate change at steady state	Which stoma accessories did you use?	APP					Subject	
			
 - Adhesive remover - Paste - Rings - Wipes - Stoma tape - Stoma belt - Hernia belt - Stoma powder - Barrier lotion/crème/spray/wipes - Cleansing wipes/cleansing spray - Odour remover - Other accessories (text) 							
										(You may tick more than one box)

CONFIDENTIAL

Type of endpoint	Group of endpoint	Description of Measurement	Derived from	Origin	Assessed by	V1	V2	V3	Calls	Product change
	Ballooning	Experience ballooning? (Yes/No) by each baseplate change at steady state	Did you experience the bag becoming overfilled with air during use (ballooning)? (Yes/No) If yes, how much did your bag become overfilled? (Not at all to very much)		Subject					X
Wear time		36. Median wear time (hours) by treatment at steady state	The median wear time is calculated by summary statistics of the individual wear times of each baseplate		Sponsor					X
	Safety endpoints	Adverse events		Sponsor calculates wear time based on photos taken by the Subject	CRF					X
		Device deficiencies			CRF	X	X	X		X
		Concomitant medication			CRF	X	X	X		X
	Not an endpoint									

CONFIDENTIAL

Page 56 of 63

CONFIDENTIAL

CONFIDENTIAL

Page 57 of 63

